4.4.2 Data Collection and Follow-up for Withdrawn Subjects

If a subject withdraws consent to participate in the study, for subject safety reasons, attempts will be made to obtain permission to collect follow up information whenever possible. Attempt will be made when the patient reports withdrawal of consent.

5 Study Drug

5.1 Description

Per Merck manual (2005):

“*CAMPRAL*® (acamprosate calcium) is supplied in an enteric-coated tablet for oral administration. Acamprosate calcium is a synthetic compound with a chemical structure similar to that of the endogenous amino acid homotaurine, which is a structural analogue of the amino acid neurotransmitter γ -aminobutyric acid and the amino acid neuromodulator taurine. Its chemical name is calcium acetylaminopropane sulfonate. Its chemical formula is C10H20N2O8S2Ca and molecular weight is 400.48.

Acamprosate calcium is a white, odorless or nearly odorless powder. It is freely soluble in water, and practically insoluble in absolute ethanol and dichloromethane. Each *CAMPRAL* tablet contains acamprosate calcium 333 mg, equivalent to 300 mg of acamprosate. Inactive ingredients in *CAMPRAL* tablets include: crospovidone, microcrystalline cellulose, magnesium silicate, sodium starch glycolate, colloidal anhydrous silica, magnesium stearate, talc, propylene glycol and Eudragit® L 30 D or equivalent. The drug product will appear in tablet form.

CLINICAL PHARMACOLOGY

Pharmacodynamics

The mechanism of action of acamprosate in maintenance of alcohol abstinence is not completely understood. Chronic alcohol exposure is hypothesized to alter the normal balance between

neuronal excitation and inhibition. *In vitro* and *in vivo* studies in animals have provided evidence to suggest acamprosate may interact with glutamate and GABA neurotransmitter systems centrally, and has led to the hypothesis that acamprosate restores this balance.

Pharmacodynamic studies have shown that acamprosate calcium reduces alcohol intake in alcohol-dependent animals in a dose-dependent manner and that this effect appears to be specific to alcohol and the mechanisms of alcohol dependence. Acamprosate calcium has negligible observable central nervous system (CNS) activity in animals outside of its effects on alcohol dependence, exhibiting no anticonvulsant, antidepressant, or anxiolytic activity. The administration of acamprosate calcium is not associated with the development of tolerance or dependence in animal studies. *CAMPRAL* is not known to cause alcohol aversion and does not cause a disulfiram-like reaction as a result of ethanol ingestion.

Pharmacokinetics

Absorption: The absolute bioavailability of *CAMPRAL* after oral administration is about 11%. Steady-state plasma concentrations of acamprosate are reached within 5 days of dosing. Steady-state peak plasma concentrations after *CAMPRAL* doses of 2 x 333 mg tablets three times daily average 350 ng/mL and occur at 3-8 hours post-dose. Coadministration of *CAMPRAL* with food decreases bioavailability as measured by Cmax and AUC, by approximately 42% and 23%, respectively. The food effect on absorption is not clinically significant and no adjustment of dose is necessary.

Distribution: The volume of distribution for acamprosate following intravenous administration is estimated to be 72-109 liters (approximately 1 L/kg). Plasma protein binding of acamprosate is negligible.

Metabolism: Acamprosate does not undergo metabolism.

Elimination: After oral dosing of 2 x 333 mg of *CAMPRAL*, the terminal half-life ranges from approximately 20 - 33 hours. Following oral administration of *CAMPRAL*, the major route of excretion is via the kidneys as acamprosate.”

5.2 Treatment Regimen

Acamprosate will be dosed at 333 mg PO TID, increased to 666 mg PO TID after 1 week if tolerated. If GFR is 30-50 ml/min, dosage will remain at 333 mg PO TID throughout the study. Treatment duration is 3 months.

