This study is a phase IIa trial of the safety of acamprosate in treating AUD in alcohol-related liver disease. Subjects will be screened for eligibility at outpatient clinic visits and during hospitalizations; interested qualified subjects will be consented and offered participation in this trial. At study enrollment, initial MELD-Na score must be less than 20 for the five individuals enrolling in the first phase of the pilot safety assessment. The second phase of the pilot safety assessment will include individuals with a MELD-Na of 20 or more at enrollment. Once consent has been obtained, baseline characteristics will be established and then patients will be initiated on acamprosate treatment. Acamprosate will be administered for three months, during which time, patients will complete monthly blood work, weekly telephone assessments for the first month, followed by telephone assessments and urine testing on a monthly basis thereafter. A final clinic visit for evaluation and collection of lab samples will be conducted at the end of the study at 3 months. Patients will be contacted by telephone at weeks 13 and 24 after study enrollment for final follow up assessments off of study medication.

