Study duration will be six months. During the study, patients will complete monthly MELD-Na labs and receive a phone call weekly for the first month, then monthly for a total of 3 months. Urine ethyl glucuronide will be done at enrollment and once monthly. Patients will then have a follow up visit at 12 weeks, with labs, urine ethyl glucuronide, vital signs and physical exam. During telephone assessments and at the follow up visit, patients will be asked about potential side effects and hepatic decompensation. Other variables to be collected at enrollment and at the 3 month visit include Child-Pugh score, West Haven grading of HE, vital signs at enrollment and current medications. At enrollment, during phone calls and at the follow up visit, patients will be asked standardized questions to assess for HE based on the abbreviated telephone version of the mini-mental state examination (MMSE). Follow up telephone visits at 13 and 24 weeks will be conducted, primarily to monitor for adverse events and alcohol relapse.

The Pennsylvania Alcohol Craving Scale (PACS) will be applied before treatment initiation, weekly for the first month on treatment, then monthly thereafter. This will include the need severity scale (mild, moderate, severe) at baseline and at each assessment by phone call and in clinic.

Alcohol use relapse will be monitored. Any amount of alcohol use as revealed during follow-up considered a relapse event. Alcohol use will be captured and categorized as none, slip (no longer drinking at most recent follow up) or sustained alcohol use (minimum 100 days drinking). Slips and sustained alcohol use will be categorized as binge drinking, frequent drinking, or both (binge drinking as more than 6 units/day for men and 4 units/day for women and frequent drinking as alcohol use in 4 or more days/week regardless of quantity per day) (Lee et al., 2018).

Basic descriptive statistics and a qualitative analysis will be performed. Analyses will be performed using SPSS 25 (Chicago, IL). Results will not contain any patient-specific information.

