3.7 Identification of Source Data

The following source data will be directly recorded on the Case Report Form (CRF):

- Vital signs
- Weight
- Clinical history
- Adverse events
- Medication list including new medications, change in medications
- Alcohol use
- Other substance use including nicotine and recreational drug use
- PACS responses and score
- MMSE responses and score
- West Haven HE grade
- Laboratory results and clinical interpretation of the values.
- Clinical significance of observations (when applicable)

The following source data will not be directly collected in the Case Report Form (CRF), but will be captured in supportive documentation (Demographics form, Concurrent Medications form):

- All data to be obtained at enrollment as detailed in 6.1.

4 Subject Selection Enrollment and Withdrawal

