4.2 Exclusion Criteria

Exclusion criteria:

- Individuals with a glomerular filtration rate (GFR) of less than 30 ml/min
- Congestive heart failure (NYHA class II or higher)
- Hypotension, requiring the use of vasoconstrictors (i.e. midodrine)
- Pregnancy, lactation or refusal to use a reliable method of birth control if a sexually active female of childbearing potential. Although no human trial data is available, animal studies suggest possible teratogenic effects of acamprosate (Merck, 2005).

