4.4 Early Withdrawal of Subjects

4.4.1 When and How to Withdraw Subjects

Patients will be withdrawn from the study prior to study completion if:

1. Subjects elect to withdraw consent
2. Subject is found to be ineligible for the protocol as per the Inclusion/Exclusion criteria.
3. Subjects experience a serious adverse event felt to possibly be related to acamprosate administration as determined by PI and/or DSMB.
4. Failure of the subject to comply with protocol requirements.
5. Exhibition of unacceptable toxicity which would make it difficult or dangerous to comply with further protocol requirements such as study visits, blood draws, etc.
6. There are changes in medical status of the subject such that the Investigator believes that subject safety will be compromised or that it would be in the best interest of the subject to stop participation in the study.

7. Death of the subject.
8. Subjects with a test consistent with pregnancy such as a positive beta-hCG.
9. Subject is lost to follow-up.
10. Any complication that requires prolongation of the hospitalization or change in treatment and in the opinion of the investigator is related to the study drug.

If subjects are withdrawn from the study, they will be replaced to ensure a total of 10 patients complete the study in its entirety. The data collected up until the time of withdrawal from the study will be included in analysis.

Follow up from subjects withdrawn from study treatment will include:

- Clinic visit at time of withdraw from study will be recommended. Beyond risk of returning to alcohol consumption, sudden study treatment termination should not include any subject safety considerations.
- Follow up phone call 3 months after withdrawal from study

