6.2 Visit 2-5

Visits 2-5 will be conducted by telephone and include data to be included on the Case Report Form including

- Clinical history
- Adverse events
- Medication list including new medications, change in medications
- Alcohol use
- Other substance use including nicotine and recreational drug use
- PACS responses and score
- MMSE responses and score
- West Haven HE grade
- Laboratory results and clinical interpretation of the values.
- Clinical significance of observations (when applicable)

6.3 Visit 6

Visit 6 will occur at week 12 of acamprosate therapy. Interval clinical history, adverse events, medication list and alcohol and other substance use will be detailed. PACS score will be evaluated. Case Report Form will be completed.

Vital signs and a physical examination will be performed. West Haven HE score will be graded and modified telephone version of MMSE completed. Blood work will be completed including a complete blood count, electrolytes, creatinine, blood urea nitrogen, total bilirubin, direct bilirubin, albumin, INR, AST, ALT and alkaline phosphatase.

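### The renal dose limits in 5.2 and 4.2 are not clearly applied to a patient already raised to 666 mg TID whose GFR falls on treatment

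*Combined protocol and SAP*

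**What the plan says.** Dosing starts at 333 mg TID and rises to 666 mg TID after one week if tolerated. The renal limit in 5.2 reads: "If GFR is 30-50 ml/min, dosage will remain at 333 mg PO TID throughout the study". The Study Summary, 1.5 and 3.1 repeat it in nearly the same words, and none adds a time point for the GFR or a method of estimating it.

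The lower limit appears only as an entry criterion, in 3.1 and again in 4.2: "Individuals with a glomerular filtration rate (GFR) of less than 30 ml/min".

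Renal function is followed during treatment. Section 3.1 states that "patients will complete monthly MELD-Na labs and receive a phone call weekly for the first month", and the schedule table after 6.5 marks creatinine at enrollment, W4, W8, W12 and W24. Sections 3.7 and 6.2 require the case report form to hold "Laboratory results and clinical interpretation of the values". Under 6.3, "Visit 6 will occur at week 12 of acamprosate therapy", and section 3 describes the calls at weeks 13 and 24 as being "for final follow up assessments off of study medication". Section 5.1 says of elimination that "the major route of excretion is via the kidneys as acamprosate".

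**The concern.** The protocol sets a lower dose at GFR 30-50 ml/min and admits nobody below 30. The drug leaves the body mainly through the kidneys, so the reason for those limits does not end at enrollment. The study recruits inpatients as well as outpatients, and its second phase takes patients with MELD-Na of 20 or more. A fall in GFR within three months is foreseeable in such patients, although the documents give no rate.

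The blood needed to see such a fall is already scheduled, but the text links no dose action to the result. Patients collect tablets from their own pharmacy and take them at home (5.4), and the schedule has telephone contacts rather than clinic visits at W4 and W8. A dose change therefore depends on the study team giving an instruction. What is at stake is dosing safety. Section 1.1 itself raises hepatic encephalopathy as a concern and reports transient diastolic hypotension after a single 666 mg dose in 12 patients with cirrhosis.

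**Working it through.** The plan gives no derived figure on this point, so the check compares the texts and adds a little dose arithmetic.

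**When the rule can act.** The dose is raised after week 1. No creatinine is scheduled then, so the enrollment value is the only scheduled one behind that decision. The next draws are W4 and W8. W12 is the end of treatment, so W4 and W8 are the only scheduled results that can guide dosing after the increase.

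**What 5.2 tells staff at W4 or W8.** The verb *remain* fits a patient who is still on 333 mg TID. It does not say that a patient on 666 mg TID is to be reduced.

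**Whether another rule supplies the action.**
- 4.4.1 item 2, "Subject is found to be ineligible for the protocol as per the Inclusion/Exclusion criteria", does not say that eligibility is re-tested on treatment. It could be stretched to GFR below 30, but not to 30-50, which is an eligible range.
- 4.4.1 item 6 and 8.5 item 5 rest on the investigator's opinion. They have no GFR threshold, and they end participation or drug rather than reduce it.
- 4.4.1 items 5 and 10 and 8.5 item 4 need unacceptable toxicity, a drug-related complication, or a CTCAE grade 3 or higher event possibly due to the drug. A GFR fall attributed to the liver disease need not meet any of them.
- The laboratory triggers in 8.1 and 8.5 are AST or ALT above 500, a MELD-Na rise of more than 5 points, and doubled bilirubin. The DSMB review in 8.5 item 6 asks whether drug-induced liver injury is suspected; it is not a renal dosing review.
- The study hold in 8.5 needs a serious adverse event to have occurred.

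None of these names an on-treatment GFR, and none sets a dose reduction.

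**Size on the literal reading.**
- Dose after the increase: 666 mg × 3 = 1998 mg/day.
- Dose the protocol sets for GFR 30-50: 333 mg × 3 = 999 mg/day.
- Ratio: 1998 / 999 = 2.
- Longest time at the doubled dose after a result in the band, taking treatment as 12 weeks: 12 − 4 = 8 weeks from W4, and 12 − 8 = 4 weeks from W8.
- For GFR below 30, the protocol sets no dose to compare with, because such patients are not admitted.

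**The case against.** The strongest reply is that 5.2 already covers the case. It ties 333 mg TID to the band for the whole study, creatinine is drawn monthly, and a hepatology team could well read this as a standing limit. That reading is fair, and it makes this an ambiguity rather than a proven hole. It does not remove the need for the wording: if a step-down is intended, stating it costs almost nothing, and if it is not, the patient stays on double the band's dose.

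A reader might infer that a falling GFR would go unnoticed, or that the patient has no protection. The documents do not support this. Results must be interpreted on the case report form, the investigator can stop the drug, and a serious adverse event or a MELD-Na rise of more than 5 points goes to the DSMB. What is missing is the defined dose action.

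A reader might also want a probability that a case occurs, or a count of excess tablets. The documents give no rate of GFR decline, so any such probability only restates an assumed rate. Cumulative tablets do not measure risk either: 5.1 gives steady state within 5 days and a half-life of about 20 to 33 hours, so the dose ratio is the relevant quantity. No exposure-toxicity relation is given, and 1.6 describes adverse events as minimal. The size of any harm is therefore not shown.

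Finally, a reader might infer that a stepped-down patient would be withdrawn under the 75% compliance limit in 5.5. Three of six tablets a day is 50%, but only if intake is counted against the superseded prescription. Read as the current prescription, the problem disappears.

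**Conclusion.** The point holds as a gap in dosing instructions. As written, the plan does not clearly require a reduction at GFR 30-50 or a stop below 30 for a patient already on 666 mg TID. On the literal reading such a patient takes twice the dose set for the band, for up to 8 weeks after a W4 result or 4 weeks after a W8 result, unless a discretionary or event-driven route intervenes.

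This rests on three things: the literal reading of *remain*, a 12-week treatment period, and the absence of a renal dosing rule in the DSMB charter or case report form. Those are attachments that were not available, so a rule held there cannot be ruled out. Confidence is moderate for that reason and because the standing-limit reading is possible.

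A reader might infer that the trial's results are compromised. They are not: safety is summarized descriptively in all subjects who received at least one dose (7.2, 7.3), and this analysis is unaffected. The change should be made for patient safety.

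**What to change.** In 5.2, with the Study Summary, 1.5 and 3.1 brought into line, state that:
- GFR is calculated by a named equation from the W4 and W8 creatinine and from any unscheduled creatinine on treatment;
- at 30-50 ml/min the dose is reduced to 333 mg TID for the rest of the study;
- below 30 ml/min the drug is stopped, with a prompt repeat test allowed to confirm the value.

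In 5.5, state that compliance is counted against the currently prescribed dose.

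The scheduled checks use blood already drawn, so the cost is amendment wording, one calculated field on the case report form, and an occasional repeat test. There are two downsides. Patients who are stepped down contribute less exposure at 666 mg TID, and a patient stopped for GFR below 30 may have to be replaced under 4.4.1 so that 10 complete. The rule would also miss a fall between the week 1 increase and W4, a gap of 3 weeks, unless an unscheduled creatinine is taken.

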5.3 Method for Assigning Subjects to Treatment Groups

n/a

5.4 Preparation and Administration of Study Drug

Subjects will collect the study drug from their local pharmacy and self-administer by mouth.

5.5 Subject Compliance Monitoring

At weekly telephone assessments for the first month, and then monthly telephone assessments and then clinic visit at 3 months, the study team will ask the patient if he or she has missed any acamprosate doses. Subjects will be asked to count their remaining pills and detail how many they were initially prescribed and when. If patients are significantly non-compliant, defined as taking less than 75% of prescribed medication, they will be withdrawn from the study.

5.6 Prior and Concomitant Therapy

All prescription and non-prescription medications will be documented at enrollment and throughout the study. There are no known significant drug interactions and no concomitant medications will be considered exclusion criteria to the study (Merck, 2005).

5.7 Packaging

Acamprosate will be administered in tablets by mouth. The drug will be picked up at the patient's preferred pharmacy. The study is not blinded. Labeling will be per manufacturer.

5.8 Masking/Blinding of Study

The study is not blinded.

5.9 Receiving, Storage, Dispensing and Return

5.9.1 Receipt of Drug Supplies

The drug will be picked up by the patient at the patient's preferred pharmacy.

5.9.2 Storage

It will be recommended that patients store acamprosate at room temperature. Merck indicates recommended storage at 25°C (77°F); excursions permitted to 15° - 30°C (59° - 86°F).

5.9.3 Dispensing of Study Drug

Regular study drug reconciliation will be performed during assessments to document drug remaining, and will be logged on the Case Report Form.

5.9.4 Return or Destruction of Study Drug

Study drug is an FDA-approved prescription medication that patients will be picking up at their local pharmacies. Should the patient stop taking the study drug for any reason, it will be recommended that they return the drug to their local pharmacy for disposal.

6 Study Procedures

6.1 Visit 1 – Screening/enrollment day

Informed consent will be obtained. Inclusion and exclusion criteria will be evaluated. Collected baseline characteristics will include patient age, sex, race, marital and employment status, education level, social support, presence of children, age of children, underlying liver disease etiology, MELD-Na score, presence of ascites, esophageal varices, spontaneous bacterial peritonitis, diabetes, corticosteroid or other medical treatment for alcoholic hepatitis (Maddrey and Lille scores if relevant), medical comorbidities, prescription and non-prescription medications. With regard to alcohol use, patients will fill out the Alcohol Use Disorder Identification Test (AUDIT) and the following history will be obtained: duration of excess alcohol consumption in years, level of alcohol consumption prior to study enrollment, interval of alcohol abstinence prior to study enrollment, family history of alcoholism, history of alcohol-related legal issues, psychiatric comorbidity (requiring medication, outpatient care or hospitalization), other addictions including smoking and number of prior rehabilitation attempts for alcohol or other addictions. The PACS questionnaire will be administered.

Vital signs and a physical examination will be performed. West Haven HE score will be graded and modified telephone version of MMSE completed. Blood work will be completed including a complete blood count, electrolytes, creatinine, blood urea nitrogen, total bilirubin, direct bilirubin, albumin, INR, AST, ALT and alkaline phosphatase. A urine ethyl glucuronide will be performed. A urine pregnancy test will be conducted before admission into the trial for women of child-bearing potential.

6.2 Visit 2-5

Visits 2-5 will be conducted by telephone and include data to be included on the Case Report Form including

- Clinical history
- Adverse events
- Medication list including new medications, change in medications
- Alcohol use
- Other substance use including nicotine and recreational drug use
- PACS responses and score
- MMSE responses and score
- West Haven HE grade
- Laboratory results and clinical interpretation of the values.
- Clinical significance of observations (when applicable)

6.3 Visit 6

Visit 6 will occur at week 12 of acamprosate therapy. Interval clinical history, adverse events, medication list and alcohol and other substance use will be detailed. PACS score will be evaluated. Case Report Form will be completed.

Vital signs and a physical examination will be performed. West Haven HE score will be graded and modified telephone version of MMSE completed. Blood work will be completed including a complete blood count, electrolytes, creatinine, blood urea nitrogen, total bilirubin, direct bilirubin, albumin, INR, AST, ALT and alkaline phosphatase.

